#### 7. STUDY DESIGN

The study type will be observational, collecting data from wearables and remote monitoring medical devices to determine correlations with primary data collected from GP surgeries attended by the participants in the course of the study.

Participants will be recruited by West Essex CCG from patients in their region who meet the study inclusion criteria.

The first phase of research with up to 100 participants will be conducted in care homes with twice-weekly visits from Health Research Assistant's (HRA) employed by the research team, equipped with a standard kit of medical devices who will ensure the devices are used appropriately to maintain data quality and who will monitor the effectiveness of the electronic devices. If care homes would rather be trained to undertake these duties using their own staff, the research team will train them and remunerate the care home for these staff costs.

The second phase of 500 participants will be conducted in participants' homes and care homes with visits from a research team HRA to ensure safe and effective use of condition specific wearable and monitoring devices when this is requested. Visit frequency will be automatically adjusted by feedback from the monitoring systems. (Typically once per week.)

The electronic devices will provide primary medical data as well as metadata regarding battery charging behaviour, adherence to study procedures, effect of active compliance management and direct feedback from the participants. The visit frequency will be adjusted to ensure maximum effectiveness of the equipment and to maximise economic benefit to allow a 'best practice' baseline to be established.

The medical devices issued to each patient will be determined by observations and data collected by the HRAs in conjunction with baseline data derived from GP data.

In **Phase 1**, all devices will be used to take measurements from all participants. Devices will be issued to HRAs who will use them to ensure correct use and valid data.

In **Phase 2**, devices will be allocated to participants based on data gathered in **Phase 1**. It is anticipated that this will demonstrate the best combinations of devices for recording health measurements for different sets of co-morbidities, and prove or disprove the following assumptions:

Clinical Research Protocol L2S2 ltd Page 16 of 38

#### Heart failure 0.44%

Weight, heart rate, BP, spO2, CO2 (using N-Tidal device if CE approved in time)

#### COPD / Asthma 0.96+0.94 = 1.9%

Peak flow, spO2, respiration rate, thermometer, CO2 (using N-Tidal device if CE approved in time)

#### Frailty / Falls / possible Syncope 1.35 + 0.33%

Heart rate, ECG, BP, spO2, CO2 (using N-Tidal device if CE approved in time)

### High frailty bedbound (3%)

Heart rate, spO2, thermometer, respiration rate, CO2 (using N-Tidal device if CE approved in time), BP

## Blood disorders / immune suppression / post chemotherapy (less than 0.1%)

Temperature, spO2, respiration rate, CO2 (using N-Tidal device if CE approved in time)

#### **Diabetes 3%**

Blood sugar, weight, temperature

#### Renal failure / Liver failure (less than 0.1%)

Weight, blood pressure, temperature, blood sugar

### % based on figures from

https://digital.nhs.uk/data-and-information/data-tools-and-services/data-services/emergency-care-data-set-ecds-data-quality#ecds-data-quality-summary-report-from-april-2018

ECDS is the new national emergency care dataset introduced into all type 1 and type 2 A&E departments in 2018 in England by [name], the Chief Investigator for this study.

## 7.1. Visit Plan

## **Phase One**

- 1. Meeting with the participant to explain the purpose and form of the study and gain consent, conducted by a member of the project team. Average meeting time 30 minutes.
- 2. Research team will talk to care home professionals to gain participant's medical history, current medication and urgent care attendance history from locally-held record.
- 3. Initial meeting between the research team Health Research Assistant (HRA) and participant (or care home employed professional and participant). The timetable for the study will be discussed and dates for routine visits will be agreed as far as is possible. The HCA will conduct risk assessments to ensure that the patient can be tested safely. The HCA will use medical devices appropriate to the participant's medical condition determined by the HCA and historical data if available. Average meeting time 30 minutes.
- 4. Follow up visits by the HCA twice weekly to take measurements from the participant using all devices. This is expected to last for approximately 12 weeks per participant, but will end when either the participant exacerbates, elects to drop out of the study or the study ends.

Clinical Research Protocol CONFIDENTIAL

L2S2 ltd Page 17 of 38

5. A final visit will be conducted at the end of the study to ensure patients understand their rights with respect to data processing and retention. Average meeting time 30 minutes.

#### **Phase Two**

- Meeting with the participant to explain the purpose and form of the study and gain consent, conducted by an appropriately trained professional at the GP surgery. Average meeting time 30 minutes.
- 2. Research team will access the participant's record in the GP's clinical system to gain participant's medical history, current medication and urgent care attendance history.
- 3. Initial meeting between the Health Research Assistant (HRA) and participant in their place of residence. The timetable for the study will be discussed and dates for routine visits will be agreed as far as is possible. The HRA will conduct risk assessments to ensure that the patient can be tested safely. The HRA will allocate medical devices appropriate to their medical condition as determined by the HRA and historical data if available. They will then explain how to use them. Average meeting time 60 minutes.
- 4. If requested by the participant, follow up visits by the HRAs will be carried out at approximately one week intervals for the remainder of the study to collect data and confirm that the participant is coping with the technology and not suffering physical or mental adverse effects. At each visit the HRA will use appropriate connected medical devices assigned to the participant to monitor both the effectiveness of equipping community staff with technology and to collect data professionally to contrast with self-measurements later in the study. Average meeting time 20 minutes.
- 5. Participants will be expected to participate for 12 weeks.
- Visits from HRAs may be offered proactively to participants by phone if they appear to be
  experiencing problems with using the devices, e.g. failure to charge the devices, improper use and
  sporadic use.
- 7. A final visit will be conducted at the end of the study to recover the equipment and ensure patients understand their rights with respect to data processing and retention. Average meeting time 30 minutes.

Participants will be encouraged to collect their own estimations of their frailty and condition (NICE guideline 56) throughout the trial for correlation against the measured data. (Participants will be asked to record data about their mood and how well they are feeling.)

### 7.2. Process for Self-Collecting Data

For participants judged to be able to self-monitor, each participant will be issued with appropriate medical devices and a single-purpose Android mobile phone that will automatically run the Reassure OneApp data collection application whenever restarted. The phone will be fitted with a data SIM provisioned with a data allowance sufficient to span the study period. The phone will not be usable for any other purpose than its use as the data collector in this study. The patient will not have to use their own mobile phone or WiFi network.

According to participants' capabilities, some will enter data from simple medical devices manually, as this is the lowest cost way of providing remote technology. Others will be issued medical devices that will connect to the phone over Bluetooth i.e. that will require no participant intervention. This will allow the effectiveness of these approaches to be evaluated across a broad cohort of participants.

The Reassure OneApp application will support simple, user friendly self-assessment questionnaires, which will be securely passed back along with the electronically collected data.

The smartphone will pass back information about the current charge of the battery to enable the HRA to swap the phone with a charged phone if the participant is confused by the charging process.

Devices will be cleaned, disinfected or sterilised as appropriate before being given to another participant.

Clinical Research Protocol L2S2 ltd Page 19 of 38

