## 3. SYNOPSIS

Clinical Research Protocol L2S2 ltd Page 6 of 38

Study title	Service demand pred	iction based on information from o	connected devices							
Internal ref. no. / short title	Service demand pred	iction based on information from o	connected devices							
Study registration	IRAS Project ID 27614	9 17-11-2019								
Sponsor	[name]	Epping,								
Funder	NHS England, [name].									
Study Design	Clinical investigation	or other study of a medical device								
Study Participants	Patients older than 65 years AND more than 2 comorbid conditions AND / OR more than one requirements for unscheduled urgent care in previous year AND / OR medium or high frailty score									
Sample Size	Phase 1: 100; Phase 2	:: 500								
Planned Study Period		dy period: 11 months rticipation period 24 weeks								
Planned Recruitment period	Phase 1: April/May 2020 Phase 2: July/August 2020									
	Objectives	Outcome Measures	Timepoint(s)							
Primary	To test the hypothesis: If information about patient behaviour, conditions and events, captured from wearables, monitors and other smart technologies	Phase 1: 100 patients:  Optimised models generate dynamic personalised monitoring plan for each participant.  Phase 2: 500 patients:	July 2020							
	can predict demand for services, then, providing these technologies to patients and using the data generated will enable providers to preempt and redirect	Model linking health outcomes to NHS activity will be developed and tested.  Confidence of correlations between measured data and observed data from actual unscheduled care data during study period.	October 2020							

	demand or design new services.						
Secondary	Dropout Percentage: Number of readings taken by patients compared to their agreed plan.	Two percentages. Participants who can / want to receive automated compliance reminders. Participants who cannot / don't want to receive automated compliance reminders.	October 2020				
	Correlation between adherence to agreed plan and the participant's frailty score.	Correlation	October 2020				
	Number of visits required for each complication group by number of comorbid conditions to achieve best value	Table / charts / recommendations with confidence levels	October 2020				

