#### 6. OBJECTIVES AND OUTCOME MEASURES

Objectives	Outcome Measures	Timepoint(s) of evaluation of this outcome measure (if applicable)
Primary Objective The purpose of the study is to find out the confidence of correlation and its statistical significance	The correlation confidence level for exacerbation prediction from data collected from medical devices in the participant's home or care home with actual attendance data obtained from GP surgeries.	End of study (study is non-interventional)
Secondary Objectives  1. Determine drop out percentage	1. Dropout Percentage: Number of readings taken by patients compared to their agreed plan.	End of study
2. Determine relationship between frailty and ability to adhere to plan	2. Correlation between adherence to agreed plan and the participant's frailty score.	
3. Determine relationship between number of co-morbidities and resource required.		

4. Determine effectiveness of different devices as predictors of exacerbation by complication group.

- 3. Number of visits required for each complication group by number of comorbidities
- 4. Correlation of each type of device for each complication group as a predictor of exacerbation (i.e determine which device(s) are most useful).

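### Section 7.2 allocates manual or Bluetooth entry by participants' capability, so it cannot support the claim that the two approaches' effectiveness will be evaluated

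*Protocol*

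**What the plan says.** Protocol section 7.2 covers participants judged able to self-monitor and sets the entry mode by what each can manage: "According to participants' capabilities, some will enter data from simple medical devices manually". It adds that manual entry is the cheapest form of remote technology. For the rest: "Others will be issued medical devices that will connect to the phone over Bluetooth i.e. that will require no participant intervention". The next sentence draws the inference: "This will allow the effectiveness of these approaches to be evaluated across a broad cohort of participants".

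No random element, crossover or group eligible for both modes is described, and no number per mode is given.

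Three other places bear on the point:
- Section 6 lists as a secondary objective "Determine relationship between frailty and ability to adhere to plan", and defines the adherence outcome as "Dropout Percentage: Number of readings taken by patients compared to their agreed plan".
- The Synopsis splits that outcome by reminder status ("Participants who can / want to receive automated compliance reminders", and those who cannot or do not want them), not by entry mode.
- Section 7 states: "The study type will be observational".

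**The concern.** A comparison of two entry modes shows the effect of mode only if the groups would otherwise have performed alike. Here the allocation rule makes them differ on capability by design. Capability is also a plausible cause of what would be measured, namely readings taken against plan, completeness and data quality. The frailty objective in section 6 shows that the protocol itself regards a closely related factor as a possible determinant of adherence. Section 7.2 foresees participants confused by charging the phone, and section 7.1 foresees improper or sporadic use of devices.

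A manual-versus-Bluetooth difference would then mix two questions: whether the mode matters, and whether more and less capable people differ. At stake is a conclusion about the cheaper manual route against connected devices that the text appears to license and the allocation cannot support.

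**Working it through.** The protocol states no effect size, group size or test for this comparison, so there is no figure to reproduce. Its only sample-size calculation (section 12.1) concerns the sensitivity and specificity of the algorithm. Everything numerical below is illustration.

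**Inputs from the protocol.** Mode is assigned by capability (7.2). Adherence is readings taken against plan (6). Phase 2 has 500 participants in total (5.2). The number per mode is not stated.

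**Assumptions.** Two capability levels; adherence treated as yes or no per participant; rate aH in the more capable and aL in the less capable; share q of more capable participants in a mode; 200 or 250 per mode; two-sided 5% test; no true effect of mode. The more capable are taken to be concentrated in manual entry. The text suggests this direction but does not state it.

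**Size of the spurious gap.** Expected adherence in a mode = q·aH + (1 − q)·aL. The gap between modes is therefore

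gap = (q1 − q2) × (aH − aL).

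Example with aH = 0.80, aL = 0.60, q1 = 0.80, q2 = 0.20:
- manual: 0.8 × 0.80 + 0.2 × 0.60 = 0.76
- Bluetooth: 0.2 × 0.80 + 0.8 × 0.60 = 0.64
- gap: 0.6 × 0.20 = 0.12

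**Chance that a 5% test declares a difference** (two-proportion normal approximation). For the example with 250 per mode, the pooled proportion is 0.70. The null standard error is √(2 × 0.70 × 0.30 / 250) = 0.0410 and the alternative standard error is √((0.76 × 0.24 + 0.64 × 0.36) / 250) = 0.0406. So z = (0.12 − 1.96 × 0.0410) / 0.0406 ≈ 0.98, giving a probability of about 0.84.

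| aH / aL | Capability mix (manual vs Bluetooth) | Gap | 200 per mode | 250 per mode |
|---|---|---|---|---|
| 80% / 60% | 100/0 vs 0/100 | 20 points | 0.993 | 0.999 |
| 80% / 60% | 80/20 vs 20/80 | 12 points | 0.75 | 0.84 |
| 80% / 60% | 60/40 vs 40/60 | 4 points | 0.14 | 0.16 |
| 80% / 70% | 100/0 vs 0/100 | 10 points | 0.64 | 0.73 |
| 80% / 70% | 80/20 vs 20/80 | 6 points | 0.28 | 0.34 |
| 80% / 80% | any | 0 | 0.05 | 0.05 |
| any | equal in both modes | 0 | 0.05 | 0.05 |

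The gap does not depend on sample size, and wherever there is a gap, the chance of declaring a difference rises from 200 to 250 per mode.

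**On a continuous adherence score.** Assume 400 home participants in total, no mode effect, and a capability-driven difference of 0.2, 0.3 or 0.5 SD. A two-sample t-test at 5% declares a difference with probability 0.51, 0.85 and over 0.99 for a 200/200 split, and 0.41, 0.74 and 0.99 for 100/300.

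**Masking.** Take the 12-point example and suppose Bluetooth truly adds 12 points for everyone. The observed rates are 76% for manual and 64% + 12% = 76% for Bluetooth, so a real benefit shows as no difference.

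**Could a later analysis repair it?** If capability fully determines mode, the groups do not overlap and no adjustment can separate the two effects. With partial overlap, adjustment needs capability to be recorded. The protocol names a frailty score but no measure of capability with the devices.

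**The case against.** The strongest reply is that this is one sentence in a section on logistics. No primary or secondary objective compares entry modes, and the adherence outcome is split by reminder status. In an observational proof of concept, the sentence can be read as describing how each approach works in the people it suits, which is a legitimate thing to report. The numbers above come wholly from assumed rates, mixes and group sizes. All of this stands as a limit on importance. It does not rescue the sentence, which presents evaluation of effectiveness as a consequence of the allocation and does not confine it to description within mode.

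Three stronger readings might be inferred, and the documents do not support them.
- *That a difference is bound to appear.* It appears only if capability also affects the outcome. That is plausible but not shown, and the bias could run either way.
- *That section 7.1 has the same fault*, because readings by the health research assistant (HRA) are to be contrasted with self-measurements while home visits depend on request or on problems. The HRA uses the devices assigned to that participant in order to "collect data professionally to contrast with self-measurements later in the study", which most naturally means the same person measured both ways, so capability differences between people do not confound it. Nor are visits confined to those cases: section 5.2 keeps twice-weekly visits for continuing care home residents, and every Phase 2 home participant has an initial HRA meeting.
- *That the commissioner's outputs rest on this comparison.* The best-practice baseline in section 7 concerns visit frequency, and section 12.5 passes on cost data without mentioning entry mode.

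**Conclusion.** The point holds in a limited form. Allocation by capability cannot support a conclusion about the relative effectiveness of manual and Bluetooth entry. The spurious component is the difference in capability mix times the effect of capability on the outcome. The allocation rule makes the first factor non-zero by design, and the second is plausible but unproven. In the illustrations with a gap, it runs from 4 to 20 points, and the chance of declaring a difference from 0.14 to 0.999. These values depend entirely on the assumed rates, mixes and group sizes and are not estimates for this trial. The primary prediction objective and the listed secondary outcomes are not affected. This is a correction to an unsupported statement, worth making because it costs almost nothing.

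**What to change.** In section 7.2, replace the sentence on evaluating the approaches with a statement such as: adherence and data completeness will be described separately for each entry mode in the participants assigned to it, and no conclusion will be drawn about the relative effectiveness of manual and Bluetooth entry. This changes neither who receives which device nor the observational character of the study, and costs only the edit.

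Only if the sponsor wants a comparative conclusion: assign mode at random among participants judged able to use either, base the comparison on them alone, and describe separately those who can use only one mode. The downsides are that some capable participants receive the dearer connected kit, and that a protocol amendment with approval under section 19.3 may be needed in a study declared observational. For a comparison outside the listed objectives, the rewording is the proportionate choice.

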## 7.3. Study flowchart

See Appendix A

#### 8. PARTICIPANT IDENTIFICATION

#### 8.1. Inclusion Criteria

Patients older than 65 years AND

more than 2 comorbid conditions AND/OR more than one unscheduled urgent care attendances in previous year AND/OR medium or high frailty score.

The study participants will primarily live in the South Uttlesford area of East Anglia, in the north of the West Essex CCG territory.

#### 8.2. Exclusion Criteria

The participant may not enter the study if ANY of the following apply:

- Children
- Individuals for whom consent cannot be obtained (i.e. individuals with mental impairments)
- Individuals who have rare chronic conditions which cannot be monitored with the devices used in the study (e.g. complex musculoskeletal conditions like ankylosing spondylitis, liver failure patients)
- Patients on palliative care
- Individuals whose wellbeing might be compromised through the measurements, such as an individual with bullous skin disease or osteogenesis, imperfect with a blood pressure cuff
- Individuals with mental health conditions whose wellbeing and care could be compromised by the introduction of measurements
- Individuals living in locations significantly far away geographically from other prospective participants (e.g. in locations where domiciliary carers might not be able to cost-effectively reach to collect measurements)
- Individuals who lose mental capacity during the study period will be removed from the study.

## 9. PROTOCOL PROCEDURES

#### 9.1. Recruitment

Participants will be selected who have a high likelihood of exacerbating during the study period, as specified in the inclusion criteria. In **Phase 1**, the potential participants will be identified by the care homes and selected participants will also be recruited by the care homes. Once the participant has agreed to take part, the research team will visit to gain informed consent.

In **Phase 2**, identification of patients will be undertaken by GP surgeries and once the participant has agreed to join the study, GP surgery staff or staff from the local Clinical Research Network (subject to confirmation) will gain informed consent.

## 9.2. Screening and Eligibility Assessment

The inclusion and exclusion criteria above will be used to identify eligible participants to approach.

#### 9.3. Informed Consent

The participant must personally sign and date the latest approved version of the Informed Consent form before any study specific procedures are performed. Where participants are unable to give consent, their legal guardian will be approached and asked if they will agree to the person taking part in the study.

Written and verbal versions of the Participant Information and Informed Consent will be presented to the participants (or legal guardians) detailing no less than: the exact nature of the study; what it will involve for the participant; the implications and constraints of the protocol; the known side effects and any risks involved in taking part. It will be clearly stated that the participant is free to withdraw from the study at any time for any reason without prejudice to future care, without affecting their legal rights, and with no obligation to give the reason for withdrawal.

The participant will be allowed as much time as wished to consider the information, and the opportunity to question the Investigator, their GP or other independent parties to decide whether they will participate in the study. Written Informed Consent will then be obtained by means of participant dated signature and dated signature of the person who presented and obtained the Informed Consent. The person who obtained the consent must be suitably qualified and experienced and have been authorised to do so by the Chief/Principal Investigator. A copy of the signed Informed Consent will be given to the participant. The original signed form will be retained at the study site.

A copy of the Informed Consent is uploaded to the IRAS site.

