#### 5.2. Method

The study will use patient data held in care home and GP records to identify potential participants. Health professionals working for the participating care homes or GP surgeries will then use inclusion and exclusion criteria to select patients for invitation to join the study. In the care home phase (Phase 1), the care home manager will sign and hand an invitation letter and Patient Information Leaflet to the potential participants whom they have identified and ask them to sign an attached form giving consent to be approached by the research team for informed consent. In Phase 2, the primary care phase, GP surgery staff will send the invitation letter and Patient Information Leaflet to potential participant and process the returned forms, booking informed consent appointments. The research team is seeking the support of the North Thames Clinical Research Network in parallel with the application to the HRA/REC; if successful, staff from the CRN will support the recruitment and consenting process in Phase 2 only.

The study cohort will be taken from those who have needed most urgent care and who have the largest number of comorbidities, as defined by the inclusion and exclusion criteria above.

**Phase 1** of the study will be conducted with up to 100 participants residing in care homes. Either Health Research Assistants employed by the research team or local care home employed professionals (the choice between these two to be at the care home's discretion) will use connected medical devices to collect data from the cohort at twice-weekly intervals for twelve weeks. In this phase **all devices will be used with all participants**.

NHS activity data will be obtained from the records held in GPs' clinical systems at the end of Phase 1 to enable models to be constructed that will test the study hypothesis and allow the mapping of chronic conditions to device types to be optimised. This will mean that in **Phase 2**, participants will only be asked to use devices that have been proved in **Phase 1** to be effective at collecting useful data relevant to their specific set of co-morbidities.

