#### 10.10. Common to all Visits

The following procedures will be checked at the start of each visit by the HCA:

- eligibility check confirm nothing has changed e.g. mental capacity
- assessment of outcome measures
- assessments of safety
- assessments of compliance with the study protocol
- general health and wellbeing of the patient

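### Sections 8.2 and 10.10 make capacity to consent a condition of eligibility, while section 9.3 offers a legal-guardian route for people who cannot consent and also demands the participant's own signature

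*Protocol*

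**What the plan says.** Section 8.2 of the protocol bars entry if any one listed criterion applies. One criterion is "Individuals for whom consent cannot be obtained (i.e. individuals with mental impairments"). The last item in the list deals with later loss of capacity: "Individuals who lose mental capacity during the study period will be removed from the study".

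Section 10.10, on procedures common to all visits, begins with "eligibility check confirm nothing has changed e.g. mental capacity". Capacity is therefore treated as a continuing condition of eligibility.

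Section 9.3 opens with a personal requirement: "The participant must personally sign and date the latest approved version of the Informed Consent form before any study specific procedures are performed". The next sentence goes the other way: "Where participants are unable to give consent, their legal guardian will be approached and asked if they will agree to the person taking part". The second paragraph repeats the guardian route: "Written and verbal versions of the Participant Information and Informed Consent will be presented to the participants (or legal guardians"). The third paragraph returns to the participant's own dated signature as the means of obtaining written consent, and provides no signature for a guardian.

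On who does what, section 5.2 says "Health professionals working for the participating care homes or GP surgeries will then use inclusion and exclusion criteria to select patients". For Phase 1, section 9.1 then says "Once the participant has agreed to take part, the research team will visit to gain informed consent". For Phase 2, section 9.1 gives the consent step to GP surgery staff or, subject to confirmation, to Clinical Research Network staff.

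**The concern.** Whether an adult without capacity may be enrolled should have one answer in a protocol, and here it has two. The first stake is the protection of vulnerable people. A consent-taker who meets someone unable to consent finds one section saying that the person is ineligible and another saying that a guardian should be asked.

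The second stake is the definition of the study population. Phase 1 recruits only care-home residents, and its data are used to build the models and to decide which devices Phase 2 participants receive. The comorbidity list that section 12.1 relies on includes dementia and Alzheimer's disease, so the question is likely to come up in practice. If the eligibility rule is unclear, so is the population to which the Phase 1 results apply.

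**Working it through.** No arithmetic applies. The document states no figure on this point and gives no share of people lacking capacity. The check is a comparison of the texts.

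| Situation | 8.2 and 10.10 | 9.3, guardian wording | 9.3, signature wording |
|---|---|---|---|
| Person cannot consent at entry | Ineligible | Guardian is asked to agree | No study procedure without the person's own signature |
| Person loses capacity during the study | Removed; capacity checked at each visit | Silent; no link to the removal rule | Silent |

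**Step 1: can 8.2 be read to fit 9.3?** One could take 8.2 to exclude only people for whom neither personal nor guardian consent is available. Its own gloss tells against this, because it equates the excluded group with people who have mental impairments, which is the group a guardian route would serve. The removal rule tells against it too: it has no exception for a participant whose guardian would agree. If guardian agreement were enough at entry, removing everyone who later loses capacity would be hard to explain. Section 10.10 points the same way by naming capacity as part of eligibility.

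**Step 2: can 9.3 be read to fit 8.2?** One could take the guardian sentence to cover people who have capacity but cannot physically sign. The text speaks of being unable to consent, not unable to sign, and the sentence before it requires a personal signature without exception. One could also take guardian agreement to be additional to the participant's signature. Then a person described as unable to consent would still have to sign a consent form.

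**Step 3: does the order of procedures settle it?** Sections 5.2 and 9.2 apply the inclusion and exclusion criteria before anyone is approached. If selection works perfectly, a person excluded by 8.2 never reaches the consent step. The conflict arises when someone passes selection and is then found unable to consent at the consent meeting. At that point 8.2 says not to enrol, the guardian wording says to ask the guardian, and the signature wording says that nothing may start.

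**Step 4: is the guardian route confined to a phase or subgroup?** It is not. Section 9.3 applies to the whole study, so the conflict covers Phase 2 as well as the care homes.

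**The case against.** The best case for leaving the text alone is that the guardian wording hardly operates. Selection under 8.2 comes first. In Phase 1, potential participants themselves sign a form agreeing to be approached. Section 9.3 then requires a personal signature before any study procedure. Followed in order, these steps would enrol nobody who cannot consent. Much of this stands: it shows that the guardian route is incomplete and that 9.3 is inconsistent within itself. It does not remove the contradiction. The guardian is mentioned twice, and the consent-taker is told that the guardian will be approached.

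A reader might infer three stronger things that the document does not support.

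- **That each care home chooses which section to follow, so that the population varies by site.** Homes select under the eligibility criteria, and in Phase 1 the research team takes consent. Variation between homes would need a home to depart from the stated selection step.
- **That people enrolled through a guardian would be withdrawn and their readings lost.** The removal rule concerns capacity lost during the study, and 10.10 looks for change since entry. For ineligibility found later, section 10.12 permits discontinuation but does not require it. The same section says that data from all enrolled participants will be analysed, and that withdrawal may lead to exclusion from certain analyses.
- **That the eligible pool changes by some particular factor.** Any such factor needs an assumed share of people without capacity and an assumed rate of guardian agreement, and the document gives neither.

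**Conclusion.** The contradiction is real and stands in the current text. Sections 8.2 and 10.10 make capacity a condition of entry and of remaining in the study. Section 9.3 provides for guardian agreement when capacity is absent, and conflicts with its own signature requirement. Selection staff and consent-takers are therefore given opposing rules, in both phases.

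The effect cannot be expressed as a number of participants or as a bias in any estimate. The conclusion rests on the wording alone and assumes only that staff may act on 9.3 as written when they meet someone who cannot consent. It is worth correcting because it concerns the protection of adults without capacity and settles who is eligible, and because correction is cheap. The document does not show which rule was intended, and this review does not say which is right.

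**What to change.** Before enrolment, reconcile 8.2, 9.3 (including both of its signature passages) and 10.10 into a single rule that applies to both phases. There are two consistent ways to do it:

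- Delete both guardian references in 9.3, so that it matches 8.2 and its own signature requirement. Sections 8.2 and 10.10 can then stay as they are.
- Keep a guardian route. Then amend the exclusion and the removal rule in 8.2, the signature requirement in 9.3 and the visit check in 10.10 to match, with ethics approval.

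The choice is for the sponsor and the ethics committee. The first option costs a few words. The second costs a protocol amendment and ethics review. Neither changes the sample size or the data collection schedule.
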